AUDIT-C	Alcohol use disorders identification test (alcohol screening tool to identify hazardous drinking)
ART	Antiretroviral therapy
CAB	Community advisory board
CITI	Collaborative Institutional Training Initiative
DBS	Dried blood spot
FGD	Focus group discussion
IDI	Individual in-depth interview
TrEAT/HWHL	Trial for Early Alcohol Treatment/Healthy Women, Healthy Living
HIV	Human immunodeficiency virus
ISS	Immune Suppression Syndrome (i.e. HIV)
IVR	Interactive voice response
Live booster	Live counselor-delivered phone-based booster call
mHealth	Mobile health
MUST	Mbarara University of Science & Technology
NIAAA	National Institute of Alcohol Abuse and Alcoholism
PEth	Phosphatidylethanol (phospholipid that can be measured in blood as a marker of prior 3 weeks' drinking)
RA	Research assistant
SMS	Short message service (text message)
SOC	Standard of care
SSA	Sub-Saharan Africa
Tech booster	Automated two-way SMS or IVR delivered booster session
Unhealthy drinking	Drinking at or above a level that increases the risk of physical or social consequences, ⁵⁹ defined here as AUDIT-C positive (score ≥ 3 for women and ≥ 4 for men)
WHO	World Health Organization

1. Study Synopsis

Alcohol consumption is a critical predictor of poor HIV outcomes such as reduced antiretroviral adherence and lack of viral suppression. Reducing unhealthy alcohol use among those with HIV may improve HIV outcomes and thus is a high priority, especially in sub-Saharan Africa (SSA) where HIV prevalence and unhealthy drinking rates are high. Multi-session interventions that combine in-person visits with booster phone calls to reinforce the in-person counseling have shown good efficacy. This project aims to compare the uptake, acceptability, efficacy, and cost in reducing unhealthy alcohol use and increasing viral suppression in a randomized controlled trial with persons in HIV care in rural Uganda (n=270). The study arms are (a) in-person counseling during 2 quarterly clinic visits plus live booster phone calls every three weeks in the interim (b) in-person counseling during 2 quarterly clinic visits plus tech (choice of SMS or IVR) boosters once to twice weekly in the interim; and (c) standard of care (SOC) control (brief unstructured advice, with a wait-listed intervention). The data collection for the study will include data to determine costs related to the intervention and control groups. In summary, results from this RCT will inform the design of a larger trial of a low-cost intervention to reduce alcohol use and increase viral suppression among those with HIV in SSA.

2. Introduction

Alcohol consumption is a critical predictor of poor of HIV outcomes, especially in sub-Saharan Africa (SSA), where both are extremely common.⁹ Heavy alcohol use has been associated with reduced antiretroviral adherence,¹⁰ decreased HIV suppression,¹¹ and increased mortality among those with HIV.^{12,13} Thus, reducing unhealthy alcohol use may improve HIV outcomes and is a high priority worldwide.¹⁴ Screening and brief counseling for alcohol use, especially multi-session approaches, have shown evidence for reducing alcohol use in resource rich settings⁵ and among persons with HIV¹⁵⁻¹⁸ with few exceptions.^{19,20} Multi-session interventions have been efficacious among persons in SSA,^{17,21,22} while those with 1-2 sessions have demonstrated mixed results.²³⁻²⁵ However, there are significant cost and human resource barriers to multiple session interventions in SSA, and it is not known whether alcohol interventions can improve HIV outcomes. Thus, the long-term goal of this research is to develop and test interventions to reduce alcohol consumption and improve HIV outcomes, that can be feasibly integrated into routine HIV care in SSA.

Multi-session interventions that combine in-person visits with booster phone calls to reinforce the in-person counseling have shown good efficacy.^{16,26} Because cell phone use in Uganda is high, phone-based booster sessions conducted in-between the in-person sessions (that coincide with regularly scheduled clinic visits) may be feasible. However, phone-based booster sessions delivered by a live counselor (“live boosters”) can be costly, time-consuming, limited to working hours, and dependent on good phone connections. Alternatively, automated cell phone-based booster sessions (“tech boosters”), can be conducted via interactive systems such as two-way Short Message Service (SMS, i.e. text messaging) or Interactive Voice Response (IVR) that allow for brief interactive sessions, with messages that are tailored to the participants’ drinking goals and gender. Such automated tailored mobile phone-based interventions have been successful in improving several health behaviors²⁷⁻³¹ in diverse populations. However, the uptake, acceptability, cost, and efficacy of live and tech booster calls for interventions for reducing alcohol use and improving HIV outcomes in SSA is not known. We hypothesize that automated mobile phone-based technology can be leveraged as an efficacious way to implement multi-session alcohol interventions at a low burden and cost to both providers and patients in low resource settings.

2.1. Specific Aims

The goal of this study is to estimate the uptake and acceptability, efficacy, and cost of methods of delivery of an intervention to reduce unhealthy drinking and HIV viral failure in a randomized controlled trial (RCT) among persons in HIV care in rural Uganda (n=270). The arms will be (1) in-person counseling during 2 quarterly clinic visits plus live booster phone calls every three weeks in the interim; (2) in-person counseling during 2 quarterly clinic visits plus tech (choice of SMS or IVR) boosters once to twice weekly in the interim; and (3) standard of care (SOC) control (brief unstructured advice, with a wait-listed intervention). We will measure outcomes as follows:

- a) **Outcome 1 is the efficacy** of an intervention to reduce unhealthy drinking and reduce HIV viral failure. This will be measured at nine months using self-report (number of drinking days in the past 21) and phosphatidylethanol (PEth), an alcohol biomarker, and viral suppression.
- b) **Outcome 2 is the uptake and acceptability** of an intervention to reduce unhealthy drinking and reduce HIV viral failure: We will examine the completion rates of the live and tech boosters, conduct post-intervention satisfaction surveys, and conduct qualitative interviews among a subsample of study participants (n=25-30) to determine acceptability and experiences with the three study arms.
- c) **Outcome 3 is the estimate of the cost of the delivery methods** of an intervention to reduce unhealthy drinking and reduce HIV viral failure: We will collect data to estimate the cost of each study arm and each mode of tech booster delivery to the patients and the clinic, including both start-up costs (e.g. initial fixed costs in tech system set-up) and maintenance costs (e.g. ongoing/recurring costs such as SMS/IVR fees, and personnel costs).

This study will be conducted in a large rural Ugandan clinic where we have 10 years of collaborative alcohol/HIV research experience. The end products of this study will be the comparisons of key outcomes to estimate effect sizes and inform the design of a future large-scale trial. The long-term aim is to implement interventions that reduce alcohol use and improve HIV outcomes feasibly and at low cost in low resource settings.

3. Background and rationale

Alcohol use has a high impact on HIV transmission and outcomes. Alcohol use has been consistently associated with reduced ART adherence,¹⁰ with the odds of missing a dose increasing with each drink.^{32,33} In a longitudinal study of 438 persons at the Immune Suppression Syndrome (ISS) HIV Clinic in Mbarara, Uganda (our proposed study site), unhealthy alcohol use (AUDIT-C score for women: ≥ 3 , for men: ≥ 4) was the strongest independent predictor of <90% adherence (adjusted odd ratio [AOR] 2.56; 95% confidence interval [CI]: 1.41-4.66) and incomplete viral suppression (AOR: 2.51, 95% CI: 1.69–3.72).¹¹ Alcohol use has repeatedly been associated with increased sexual risk behavior and HIV transmission.³⁴⁻⁴⁰ Approximately 25% of persons with HIV worldwide are unhealthy drinkers.⁴¹⁻⁴⁷ Thus, unhealthy alcohol use is a significant barrier to suppressing HIV, and reducing unhealthy drinking is consistent with NIH HIV priorities.

Multi-session in-person alcohol interventions are efficacious but not scalable. Counseling interventions to reduce alcohol consumption from risky levels before more severe consequences occur have shown efficacy to reduce drinking by 15-30% one-year post intervention,^{5,48-55} and multi-session interventions have the strongest evidence of an effect on alcohol consumption.⁵ In the few alcohol intervention trials conducted in SSA, the most consistent evidence for alcohol intervention efficacy was for interventions delivered over 4-6 in-person sessions,^{17,21,22} as compared to those with one session,^{23,24} or one session followed by a booster call.²⁵ Multi-session alcohol interventions for those with HIV conducted worldwide have been successful at reducing alcohol use,^{15-18,22} with only a few exceptions.^{19,20} Yet multi-session interventions with several in-person visits are unlikely to be scalable or cost-effective in SSA.⁸

Cell phones may be useful for multi-session interventions. We (co-investigators [name] and [name]) recently tested a multi-session alcohol intervention for women with HIV in Baltimore (the Healthy Women Healthy Living [HWHL] study),¹⁶ adapted from Project TrEAT (Trial for Early Alcohol Treatment) which included both men and women.²⁶ Both interventions were comprised of two brief in-person sessions, separated by a month, each followed by live phone-based booster sessions 2-3 weeks later; both were efficacious in reducing drinking.^{16,26} Phone-based counseling has been successful in several behavior change interventions, including alcohol reduction,⁵⁶ smoking cessation,⁵⁷ reduction of depressive symptoms,⁵⁸ and increasing physical

activity,³¹ suggesting phones may provide an opportunity to increase the number of intervention sessions.

Cell phone usage has risen steadily in Africa,⁶⁰ cell phone ownership in the Mbarara ISS Clinic reached 82% at the end of 2015, with another 14% having access to a shared phone ([name], personal communication). Basic cell phones predominate and are inexpensive in SSA (ranging from \$15-\$20) with low cost pay-as-you-go plans, and it is free to receive calls and SMS. Thus, cell phones hold promise for delivering interventions to broad populations in SSA, such as persons with HIV.⁶¹

Automated interactive (2-way) interventions also hold promise.

SMS Health interventions that allow for a 2-way interaction, delivered via SMS (up to 160 characters, available on all cell phones) or multimedia messaging service (MMS, mostly available on smart phones) have proliferated in recent years (albeit mostly in high-income countries⁶²); a review of 15 systematic reviews/meta-analyses covering 89 unique SMS/MMS trials was recently published.²⁸ The authors found overall positive effects on medication adherence, smoking cessation, diabetes management, weight loss, and physical health, although limitations to the findings were cited. A small number of studies have examined using SMS to reduce alcohol use.⁶³ These studies, conducted mostly among university students and young adults, have shown feasibility^{64,65} and promising results.^{2,3,66-68} SMS is available on all phones and used by most (80%) cell phone users.⁶⁰ However, the usefulness of SMS may be limited among those with low literacy. Reading literacy is 78% among adults in Uganda⁶⁰ and 71% in our study population, thus SMS may be challenging for a significant fraction of the target population.

IVR IVR is an automated mobile phone-based platform that differs from SMS in that the participant hears rather than reads a message, so IVR is advantageous for those who are not literate. IVR technology allows bi-directional communication, similar to SMS. Participants respond to questions by pressing buttons on the phone keypad. IVR has been used as a way to collect daily alcohol and substance use data,⁶⁹⁻⁷¹ and has shown promising results for alcohol interventions⁷² and for daily alcohol self-monitoring.^{15,73-76} A recent trial of an intervention to increase physical activity among older adults, found that a 2-way IVR intervention performed as well as a live phone-based counselor and significantly better than the control.³¹ Thus, IVR could be a promising mode of automated delivery of phone-based booster sessions in low literacy settings.

Comparison of live versus automated booster calls. There are several strengths and limitations to consider for live versus automated interventions, including issues of network quality, message length, confidentiality, and literacy requirements (Table 2). While overall, analyses suggest that interventions with live counselors have better results than technology delivered interventions,⁷⁷⁻⁸⁰ it is not known how these modes of delivery compare for booster session delivery. There is high enthusiasm for technology-based interventions⁸¹ and several studies using SMS or IVR for improving ART adherence in SSA have been quite successful.^{82,83} Advantages to 2-way automated messaging (SMS or IVR) include flexibility in the timing of the messages, standardization, and low cost, while disadvantages include the limited ability to personalize and, for SMS, literacy (Table 2). Live boosters allow for a more personal experience but have high counselor time and cost, may depend on phone network quality, and have low flexibility in timing for the calls. Thus we feel that there is considerable equipoise between the methods and impetus to explore both tech and live booster calls, and gather preliminary data on the uptake, acceptability, effectiveness, and cost of these methods.

Cost estimates for mobile technology interventions in SSA are scarce. Few studies have examined the costs associated with mobile phone-based interventions,^{28,61} via live or tech delivery, although screening and brief interventions have been shown to be cost effective in the primary care setting in the US.^{48,84,85} The preliminary cost data will guide short-term decisions on which interventions to include in a future larger trial, while long-term implementation decisions will also ultimately depend on cost.⁸

Valid measurement of unhealthy alcohol use is needed. In trials aiming to reduce certain behaviors, self-report of those behaviors can be especially problematic.⁸⁶⁻⁸⁸ For example, a recent alcohol pharmacotherapy trial showed declines in self-reported heavy drinking days in both the treatment and the control arms, while PEth declined only in the treatment arm.⁸⁹ The authors suggested that the control arm may have experienced an effect due to knowing that the intervention was to reduce alcohol (demand characteristics), and recommended using PEth in addition to self-report in future alcohol intervention trials.⁸⁹ PEth is a phospholipid which is formed only in the presence of alcohol and thus is highly specific.⁹⁰ PEth is the most sensitive medium-term biomarker,⁹¹ and PEth levels have been well correlated (Spearman's $r = 0.6-0.8$) with level of consumption in controlled studies.⁹²⁻⁹⁵ We found that PEth was 95% sensitive and 73% specific for detecting prior 21 day heavy drinking, and highly correlated with the number of drinking days in persons with HIV in Uganda⁹⁵ we have subsequently used PEth to confirm suspected under-reporting in that setting.^{96,97}

Table 1. Comparison of live versus automated phone-based counseling. Advantages highlighted and bolded.

	Live phone counseling	2-way SMS	2-way IVR
Importance of reading literacy	None	High	None
Importance of technical/phone literacy	Low	Medium	Low
Air time needed to respond to messages	No	Yes	No
Dependence on phone network quality	High	Low	Medium
Limits to length of message	None	160 chars	None
Ability to verify persons answering	High	Need PIN	Need PIN
Uniformity of messages*	Low	High	High
Ability to personalize (i.e. use names)	High	High	Low
Ability to tailor messages	High	Medium	Medium
Two-way capability	High	Medium	Medium
Messages remain on phone*	No	Yes	No
Capability for participant to communicate with the counselor	High	Medium, delayed	Medium, delayed
Flexibility in timing of boosters	Low	High	High
Flexibility in timing of attending to the message	Low	High	Medium: call back option
Anticipated cost per person	High	Low	Low

*May be an advantage or a disadvantage

3.1. Preliminary Studies

Target population characteristics. We have been conducting studies of alcohol consumption among persons with HIV in Uganda since 2006.^{66,96,99-104} Self-reported current alcohol consumption among persons with HIV in Uganda ranges from 18% to 31%,¹⁰¹⁻¹⁰³ an under-estimate based on our studies of self-report compared to PEth.^{96,99-101} We recently conducted longitudinal cohort studies of persons who reported any prior year alcohol consumption at HIV clinic entry (Biomarker Research of Ethanol Among Those with HIV [BREATH], R01 AA018631) and of the effect of unhealthy alcohol use on HIV disease progression prior to ART initiation (U01 AA020776), as part of the NIAAA Consortiums for HIV/AIDS Alcohol Research Translation (CHAART).⁷ In total, 751 persons were enrolled, 465 reported current drinking, and 242 reported unhealthy drinking via the AUDIT-C (≥ 3 for women, ≥ 4 for men). Among these, the level of drinking was high (Table 3).

Need for intervention. The participants in the BREATH study were followed quarterly after HIV clinic entry, to determine how unhealthy alcohol consumption, (AUDIT-C positive or PEth ≥ 50 ng/ml), changed over one year. We found that overall, there was no change in unhealthy alcohol consumption (per-month AOR for unhealthy drinking: 1.01; 95% CI: 0.94-1.07). However, there was a declining trend prior to ART (per-month AOR 0.91; 95% CI: 0.83-0.99) but increases after ART start (per-month AOR 1.11; 95% CI: 1.01-1.22). This pattern of declining and then rebounding unhealthy use after ART initiation suggests that reductions in unhealthy alcohol use are possible, but a systematic intervention is needed to sustain reductions over time. These results were supported by qualitative work in the same study, in which 59 participants participated in semi-structured interviews to examine the social, contextual, and psychological factors influencing attempts to change alcohol use over the year.¹⁰⁵ Reasons to decrease alcohol consumption included threats to and impact on financial security, interference with fulfillment of social obligations, and threatened social standing in the community. Reasons for continued or resumed drinking, which will be addressed in the intervention adaptation, included peer pressure to drink, social inclusion, stress relief, and overall enjoyment of consuming alcohol. Motives to

drink and to reduce drinking are similar to those found in other populations,¹⁰⁶ including persons with HIV,^{107,108} suggesting that interventions that were successful elsewhere can be adapted to this setting.

Feasibility of tech boosters for alcohol interventions. Drs. [name] and [name] have recently adapted the TrEAT/HWHL intervention for digital delivery (computer-based with SMS and IVR booster sessions) among sexually transmitted disease clinic patients in Baltimore (R01AA018632). Initial SMS response rates (75% of participants responded to SMS messages not requiring a response) demonstrate high engagement. [name] et al. recently developed and tested a 2-way SMS-based intervention that increased postnatal HIV clinic visits by women and their infants in Kenya.²⁹ Messages were developed and piloted within a theoretical framework, via a series of FGDs and IDIs, using a strategy similar to that proposed here.

4. Study design overview

This study is a randomized controlled trial (RCT) to compare the uptake, acceptability, cost and efficacy in reducing unhealthy alcohol use and increasing viral suppression by study arm among persons in HIV care in rural Uganda (n=270). The RCT study arms are (a) in-person counseling during 2 quarterly clinic visits plus live booster calls every 3 weeks in the interim, (b) in-person counseling during 2 quarterly clinic visits plus tech (SMS or IVR) boosters twice weekly in the interim, and (c) standard of care control (brief unstructured advice, with a wait-listed intervention). We will obtain estimates of uptake, acceptability and cost, as well as efficacy in reducing alcohol use and decreasing viral failure for each study arm. We will utilize an alcohol biomarker, phosphatidylethanol (PEth) in addition to self-report in measuring reductions in alcohol use, and we will measure viral suppression at follow up study visits (6- and 9-month visits for PEth, and 9-month visits for HIV VL). The goal is to inform the design of a future large-scale trial and, ultimately, implementation.

The trial will be conducted during a 9-month period with the intervention occurring in the first 3 months with 6 months of follow-up. The primary outcomes will be measured 6 and 9 months post-randomization. Outcome 1 is alcohol use reduction measured by the number of drinking days (of prior 21) at 6 and 9 months. HIV viral suppression at 9 months is a secondary outcome. We will also measure intervention acceptability and uptake, as well as cost, by study arm.

4.1. Study setting

The EXTEND study will be conducted at the Immune Suppression Syndrome (ISS) Clinic of the Mbarara Regional Referral Hospital (MRRH) in southwestern Uganda. The adult HIV prevalence in Southwest Uganda is 8% and heavy alcohol use is common while other substance use is rare. There are over 12,000 active patients at the ISS Clinic; 25% are current drinkers. The ISS Clinic and pharmacy use electronic medical records (EMR) that will be leveraged for patient recruitment, and tracking.

5. Study Procedures

5.1. Recruitment

Participants will be recruited from the electronic medical records of persons attending the Mbarara ISS Clinic. The AUDIT-C is conducted routinely at the initial clinic visit. A clinic staff member who is also a member of the research team, e.g. the screener, record room staff, will initially approach those meeting these criteria. Persons meeting the initial eligibility criteria will be asked by the clinic staff member if they are interested in taking part in a research study. Those who agree will be referred to the study RA to determine further eligibility criteria and provide informed consent.

5.2. Screening

Participants will be recruited from the ISS clinic by a clinic staff member. This person will examine clinic records to identify those who are coming in for appointments who meet study criteria. Persons meeting these pre-screening eligibility criteria will be invited to meet with a study RA. Those who agree will be screened to determine further eligibility criteria by the RA. Following the screening, the RA will seek informed consent from individuals who meet the inclusion criteria below for further study participation. The baseline visit will include collection of tracking information, a baseline survey, and blood draw. Participants randomized to the intervention arms of the study will complete session 1 of the intervention.

5.2.1. Inclusion criteria

Trial inclusion criteria include:

- a) HIV-infected adult (≥ 18 years) attending the Mbarara ISS Clinic;
- b) Prescribed ART for at least 6 months (confirmed via clinic records);
- c) Consume alcohol at unhealthy levels (AUDIT-C score ≥ 3 for women, ≥ 4 for men, based on the prior 3 months);
- d) Have daily cell phone access;
- e) Fluent in Runyankole (the local language) or English;
- f) Lives within 2-hour driving distance or 60 km of the study site (Mbarara ISS Clinic)
- g) Be willing and able to agree to the study procedures.

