5.9.1. Primary analyses

Efficacy analyses

The analysis for primary outcome variable 1 (alcohol reduction) will measure the number of drinking days (of the prior 21) at six months and nine months, in pairwise comparisons of the study arms, controlling for baseline days drinking (of the prior 21).¹⁴⁹ The analyses will be conducted as intention-to-treat, and we will use Poisson or negative binomial regression for the count data, i.e. the number of drinking days at 6 and 9 months, controlling for baseline days drinking. The PEth level will be transformed to log10 PEth before analyses, based on PEth's highly skewed distribution and we will use linear regression for this outcome.

The analysis for primary outcome variable 2 (HIV viral suppression) will use logistic regression to compare the proportions with viral load<500 copies/ml, controlling for baseline viral load. We will adjust these analyses for baseline characteristics that exhibit imbalance between groups (based on a p-value ≤ 0.1 in comparisons of potential confounders listed in Table 3).

Secondary outcomes: Other exploratory outcomes will include CD4 cell count and ART adherence.

Missing data We will evaluate differences in baseline characteristics between those lost to follow-up versus those who are retained.¹⁵² If it is reasonable to assume that data are missing at random, multiple imputation methods will be applied to account for the missing data.^{152,153} We will also consider pattern mixture models,¹⁵⁴ which are applicable when the data are missing not at random.

Statistical power: With a sample size of 90 in each arm, assuming 90% 9-month retention, using a simplifying t-test for power calculations, we will have 80% power to detect a difference in the number of drinking days in the prior 21 between two study arms at nine months of ≥ 2.4 days, i.e. nearly 1 fewer day per week, as statistically significant ($\alpha=0.05$) assuming that the mean number of drinking days in the prior 21 in the control group is 7 (standard deviation is 5.5, based on prior data). Given that this is a pilot study we will not adjust for multiple comparisons.

Booster uptake and satisfaction analyses

Analyses We will calculate 95% confidence intervals for the outcomes listed above. We will conduct preliminary tests of whether the mean completion proportions and satisfaction scores differ by booster arm (live versus tech) by conducting 2-sample tests (t-test or Mann-Whitney).

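### Section 5.9.1 gives the month-9 viral-suppression model no expected failure rate and no sparse-data method; if failures are few, its odds ratio will be somewhat inflated or sometimes not estimable

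*Combined protocol and SAP*

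**What the plan says.** All references are to the combined protocol and SAP.

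- **Model.** For viral suppression, section 5.9.1 "will use logistic regression to compare the proportions with viral load<500 copies/ml, controlling for baseline viral load". It also adjusts for baseline characteristics that differ between arms, "based on a p-value ≤ 0.1 in comparisons of potential confounders listed in Table 3".
- **Size.** The power paragraph of 5.9.1 starts "With a sample size of 90 in each arm, assuming 90% 9-month retention". That leaves 90 × 0.90 = 81 per arm. Power is given for drinking days only.
- **Population.** Section 5.2.1 requires "Prescribed ART for at least 6 months (confirmed via clinic records" and sets no viral-load criterion. It also requires that participants "Consume alcohol at unhealthy levels (AUDIT-C score ≥ 3 for women, ≥ 4 for men, based on the prior 3 months". Section 3 reports that, at this clinic, such drinking was associated with "incomplete viral suppression (AOR: 2.51, 95% CI: 1.69–3.72".
- **Purpose.** Section 2.1 states: "The end products of this study will be the comparisons of key outcomes to estimate effect sizes". The opening line of 5.9 says much the same.

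The documents give no expected viral failure rate, no power or precision for this outcome, no absolute-difference summary, and no fallback for empty cells or non-convergence.

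**The concern.** Logistic regression, as normally understood, means maximum likelihood. With few events per model term it pushes the log odds ratio away from zero, and if one arm has no failures the odds ratio is infinite. People on ART for six months or more may be largely suppressed, so both are possible here. The covariate rule adds to the load. I count about 24 candidate baseline variables in Table 3, so about 24 × 0.1 = 2.4 would enter by chance, making four or five terms with arm and baseline viral load.

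The estimate matters because the trial exists to supply effect sizes and a significance test on this outcome will have little power. If the method fails or drifts, the viral part of that product is weakened, and the plan does not say what would be reported instead.

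**Working it through.** **1. The plan's own power figure.** For drinking days, SE = 5.5 × √(2/81) = 0.864 and 2.4/0.864 = 2.78. Power is Φ(2.78 − 1.96) = 79% (78.8% by exact t-test). The stated 80% is reproduced, so 81 per arm is the right base.

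**2. Expected failures.** Control failure rates are my assumption. For the true odds ratio I take 1/2.51 = 0.40, the association in section 3 fully reversed. At 10% control failure, the control odds are 0.111; 0.111 × 0.398 = 0.0443, so active-arm failure is 4.2%. Expected failures, control + active:

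- 5%: 4.0 + 1.7 = 5.7
- 10%: 8.1 + 3.4 = 11.5
- 15%: 12.2 + 5.3 = 17.5
- 20%: 16.2 + 7.3 = 23.5

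**3. An arm with no failures.** At 5% control failure and odds ratio 0.40, active-arm failure is 2.05%. P(none) is 0.9795^81 = 0.186 in the active arm and 0.95^81 = 0.016 in control. P(either) = 1 − 0.814 × 0.984 = 20%. At odds ratio 0.60 (active-arm failure 3.06%) the same sum gives about 9.5%. At 10% control failure and odds ratio 0.40 it is 3%.

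**4. Bias and estimability, by simulation (81 per arm).**

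*Setup A:* true odds ratio 0.40 or 0.60, odds ratio 8 for being unsuppressed at baseline, three null covariates. At 10–20% control failure, two independent runs gave log odds ratios 7–15% and 8–17% too large. At 5%, about 25–35% of maximum-likelihood fits were not estimable. Firth averaged 0.97–1.04 of the true log odds ratio at 10–20%, with root mean squared error 6–13% lower.

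*Setup B:* true odds ratio 0.50, two noise covariates, 40%, 60% or 80% of baseline failures persisting. Ranges are over persistence:

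| Control failure | Not estimable or not converged | Log odds ratio error among usable fits | Firth mean odds ratio |
|---|---|---|---|
| 3% | 50–76% | −52% to −31% | 0.58–0.67 |
| 5% | 18–53% | −36% to +7% | 0.50–0.60 |
| 10% | 2–19% | +4% to +16% | 0.49–0.53 |
| 15% | 0–6% | +9% to +18% | 0.48–0.50 |
| 20% | 0–1% | +6% to +10% | 0.50–0.51 |
| 30% | about 0 | +2% to +7% | 0.50–0.52 |

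The second column counts every non-converged fit, including those where the baseline term caused the failure. Firth itself converged in at least 98% of runs at 5% and above, and in 91–95% at 3%.

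**5. Bias against sampling error.** With odds ratio 0.40 and 10% control failure, the SE of the unadjusted log odds ratio is √(1/8.1 + 1/72.9 + 1/3.4 + 1/77.6) ≈ 0.66. The 95% interval is the estimate multiplied or divided by exp(1.96 × 0.66) ≈ 3.7. At 20% failure the SE is 0.48 and the factor 2.5. A bias of 7–17% of |ln 0.40| = 0.92 is 0.06–0.16, or about 0.1–0.3 SE.

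**6. Power.** By Φ(difference/SE − 1.96), power for odds ratio 0.40 is about 17%, 30%, 41% and 52% at 5%, 10%, 15% and 20% control failure. For example, at 10%: 0.0576/0.0402 − 1.96 = −0.53, which gives 30%.

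**The case against.** **Few failures are not established.** A reader might infer from the ART criterion that failures will be rare. The documents do not say so. The same criteria select unhealthy drinkers, and section 3 calls unhealthy drinking the strongest independent predictor of incomplete suppression at this clinic. This stands, and it makes the point conditional on the rate.

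**The bias is small next to the noise.** This also stands. A reader might infer that the next trial would be 13–27% too small (1 − 1/1.07² to 1 − 1/1.17²). That would follow only if planners took one pilot estimate at face value despite an interval spanning a factor of 2.5–3.7 either way.

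**Firth has limits.** In setup B at 5% failure its mean odds ratio reached 0.60 against a true 0.50, losing about a quarter of the log odds ratio. At 3% the loss was 21–42%. It gives a usable estimate where maximum likelihood often gives none, but it adds no information.

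**Scope.** Section 4 calls viral suppression secondary, while 5.9.1 treats it as a second primary outcome. The covariate rule covers potential confounders, which may be fewer than every Table 3 entry. The plan does not make the odds ratio its only summary. These points limit the weight of the issue; they do not supply a sparse-data provision.

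**Conclusion.** The gap is real and its consequence depends on a failure rate that the documents do not give.

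- **10–20% control failure:** the log odds ratio is overstated by roughly 7–17%, about 0.1–0.3 SE at an odds ratio of 0.40.
- **About 5% or below:** the arm effect is often not estimable, with an empty arm in about 9–20% of trials at 5% and more adjusted fits that do not converge. Finite fits are not reliably inflated here; at 3% they lean toward 1.
- **30% or more:** the problem is small.

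A reader might conclude that the trial's effect size will be inflated or unobtainable. The documents do not support that: at 15% or more the model nearly always fits, and the drinking-days effect is untouched. Imprecision is the larger problem for this outcome.

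The figures assume 81 analysed per arm, a binary baseline viral-load term, two or three extra covariates, and true odds ratios of 0.40–0.60. The change is worth making because it costs little and performs at least as well as the planned method across 10–30% failure.

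**What to change.** In section 5.9.1, for viral suppression:

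1. Fit the model by Firth-penalised logistic regression, with profile penalised-likelihood confidence intervals.
2. Alongside the odds ratio, report the between-arm difference in proportion suppressed with a 95% CI. The difference stays defined when an arm has no failures. It also shows the scale plainly: 90% against 94.7% suppressed is an odds ratio of 2.0 but a difference of 4.7 points.
3. State the assumed failure rate, or a range, and the precision it implies.
4. State that this outcome is interpreted from the estimate and its interval, and that a non-significant result will not be reported as no effect on viral failure.

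The cost is SAP wording and a widely available software option, with no new data or participants. The downsides are some shrinkage of the odds ratio toward 1 when failure is about 5% or below, an intercept correction if predicted proportions are taken from the Firth model, and a little more work to pool results under the planned multiple imputation.
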